9.0 Procedures Involved

9.1 Study design:

The clinical trial will be an assessor-blinded prospective randomized cross-over trial wherein participants with unilateral transfemoral amputation will be randomized to using one of two socket conditions (i.e., sub-ischial or ischial containment) before crossing over to the other socket condition. Random allocation (computer-generated) utilizing blocks of random size will be used to assign the initial treatment condition. The trial will be balanced such that all subjects will receive all treatments (i.e., both socket conditions) and that all subjects will participate for the same number of periods (i.e., two).

9.2 Research procedures:

The study is composed of two phases for each socket: socket preparation and then 6 weeks of socket wear during which 3 identical data collection sessions will be held (week 1, 3 weeks and 6 weeks).

Socket Preparation Phase:

All sockets will be made following standard clinical procedures that include taking an impression (i.e., cast) of the residual limb, converting the negative residual limb model to a positive mold made of plaster of Paris, rectifying the positive mold using the rectification procedures specific to each socket design, thermoforming a clear diagnostic check socket, and ultimately manually fabricating, fitting and aligning a definitive socket.

Data Collection:

At each visit we will collect the following data:

1. *Socket Comfort Score (SCS)* – The SCS is a simple rating of comfort on a scale of 0 to 10 where 0 is the most uncomfortable socket fit imaginable and 10 is the most comfortable socket fit.
2. *Orthotic and Prosthetic Users' Survey (OPUS)* – The OPUS is a set of surveys that evaluate the subject's perception of function, quality of life, and satisfaction with the socket and prosthesis. The lower extremity function survey has 20 questions rated on a 5-point scale; the quality of life survey has 23 questions rated on a 5-point scale; and the satisfaction with device survey has 9 questions rated on a 5-point scale.

PROTOCOL TITLE: Functional Performance Evaluation of the Northwestern University Flexible Sub-Ischial Vacuum (NU-FlexSIV) Socket for Persons with Transfemoral Amputation

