A cross-over study has two advantages over both parallel and non-crossover longitudinal study designs. First, the influence of confounding covariates is reduced because each cross-over patient serves as their own control. This is particularly important given the custom nature of prosthetic interventions. Second, cross-over designs can be statistically efficient, requiring fewer subjects than non-cross-over designs. This is of particular benefit for prosthetic studies given the cost, time and effort involved in providing custom prosthetic devices for use every day during the study. Cross-over studies are typically subject to order effects, which in this case the most likely is shrinking of the residual limb during the first intervention phase. This shrinkage is typical of what happens any time a new, more tightly fitting socket is provided to a person with amputation. However, the effect of shrinkage is accounted for by having casting and fabrication of the second test sockets occur after data collection in the first socket is completed. While a washout period is not strictly necessary, it is effectively included as subjects will need to transition back to their usual, pre-study socket/prosthesis while the second test socket is fabricated.

Socket allocation will be concealed from the investigators until after a subject is enrolled. The starting socket design will be enclosed in sequentially numbered, opaque, sealed envelopes. Envelopes will be opened sequentially and only after the participant's name and other details are written on the appropriate envelope.

Blinding of prosthetic interventions is challenging given that they are devices that must be custom-fabricated and donned each day by the subject. Hence, for this study only the assessor, our research engineer, [name], will be blinded. To maintain blinding the assessor will remain uninformed in any aspect of the study except administration of performance and patient-reported measures and processing motion analysis data.

- The assessor will not be present for motion analysis data collection given that this requires exposure of the prosthesis and socket for appropriate marker placement. Since all that is recorded is the location of retro-reflective markers on the subject, it is not

[figure not shown]

Figure 6 Motion analysis data processing window.

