PROTOCOL TITLE: Functional Performance Evaluation of the Northwestern University Flexible Sub-Ischial Vacuum (NU-FlexSIV) Socket for Persons with Transfemoral Amputation

possible to tell while processing the motion analysis data what socket the subject was wearing because the data is viewed only as a stick figure (Figure 6).

- Performance and patient-reported measures can be administered fully clothed, which will disguise the socket being tested. During these assessments, subjects will be instructed not to reveal to the assessor which socket they are wearing.

Given the customized, manually-fabricated nature of prosthetic sockets, each test socket will be provided to study subjects by a separate Certified Prosthetist known for their skill with the particular socket design. This will ensure that each socket is the best and most consistent example of each particular socket design.

Since accommodation to sockets is unknown, data will be collected at baseline (within one week of definitive socket fitting) and after 3 and 6 weeks of every day socket use. These time points were chosen to enhance subject retention. Since we anticipate that one socket will be more comfortable than the other, it is possible that some subjects will find it challenging to use the less comfortable socket for a long period of time. By keeping each testing phase reasonably short (i.e., 6 weeks) we hope to retain as many subjects as possible. Additionally, by collecting data at 3 time points, we hope that if subjects are unable to continue to wear the socket for the entire six weeks, we will have initial and intermediate times points for comparison.

Step activity monitors attached to the test prostheses will allow monitoring of every day socket use. This will provide information regarding compliance with use of each prosthesis. As a secondary consideration, it will allow us to check whether there is a relationship between comfort and step activity.

When assessing the biomechanics of walking data consistency will be assured by (1) collecting all data in the same laboratory using the same instrumentation; (2) having marker placement conducted by the same experienced person who has been shown previously to have high reliability in this task; and (3) having a single person post-process all the data.

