- The study team will meet four times a year to discuss the project and ensure that all persons assisting with the research are adequately informed about the protocol, the research procedures, and their duties and functions.

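### The only blinded assessor also collects the comfort and satisfaction ratings, which weakens the blinding of the timed performance tests

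*Combined protocol and SAP*

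**What the plan says.** Section 9.1 describes the trial as assessor-blinded. Section 11.4 explains that only the assessor, a research engineer, is blinded: "the assessor will remain uninformed in any aspect of the study except administration of performance and patient-reported measures". The same exception covers the handling of gait data. The patient-reported measures are the 0 to 10 Socket Comfort Score and the OPUS. Section 9.2 describes the latter: "The OPUS is a set of surveys that evaluate the subject's perception of function, quality of life, and satisfaction with the socket and prosthesis". Both are collected at three sessions per socket, along with the three timed tests.

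Section 11.4 gives three safeguards:

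- Clothing: "Performance and patient-reported measures can be administered fully clothed, which will disguise the socket being tested".
- An instruction: "subjects will be instructed not to reveal to the assessor which socket they are wearing".
- Absence from gait capture: "The assessor will not be present for motion analysis data collection". The assessor later sees the gait data only as a stick figure.

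On the expected result, Hypothesis 1 (section 1.2) names the NU-FlexSIV as the more comfortable socket. Section 11.4 explains the short wear periods with the words "Since we anticipate that one socket will be more comfortable than the other". Section 20.2 adds that the study team meets four times a year to "ensure that all persons assisting with the research are adequately informed about the protocol, the research procedures, and their duties and functions".

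**The concern.** The safeguards hide the socket from view and stop the subject from naming it. They do not hide how the subject rates it. Under the trial's own primary hypothesis, that rating points towards the allocation. By period 2 the assessor may hold the same subject's comfort and satisfaction answers for both sockets while running that subject's timed tests.

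What is at stake is Hypothesis 2c: sit-to-stand, Four Square Step and T-Test times. The Socket Comfort Score comes from the unblinded subject, so assessor blinding neither protects nor harms the primary endpoint. Gait processing has the stick-figure view. The timed tests are where the assessor-blinded label carries most weight, because the assessor administers them in person. An assessor who suspects which socket is worn could, without meaning to, run or score the tests a little differently.

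**Working it through.** **Inputs from the documents.** Section 11.2: paired effect d = 0.754 on the Socket Comfort Score, two-sided alpha 0.05, power 0.95, N = 25. The effect comes from six persons who wore a containment socket and a wider version of it, not the NU-FlexSIV. Section 11.1: three timed tests, paired t-tests, Bonferroni. I take the family as these three tests, so alpha = 0.05/3 = 0.0167 each.

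**Assumptions, not in the documents.** The within-subject correlation rho between the two sockets' scores; the correlation c of the socket difference across visits; the size b of any assessor bias, in SD units of the paired time difference.

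1. *The plan's own figure.* Noncentral t with n - 1 degrees of freedom and noncentrality d x sqrt(n): n = 25 gives power 0.951 and n = 24 gives 0.942. The stated 25 reproduces, and nothing below changes it.

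2. *Guess accuracy with one score per socket known.* The rule is that the higher score marks the NU-FlexSIV. P(correct) = Phi(d) = Phi(0.754) = 0.775. With scores rounded to whole points, ties split, and mean differences of 1 to 3 points (the range section 11.1 quotes for the score's sensitivity to socket change), it is 0.76 to 0.77.

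3. *Three visits per socket.* P(correct) = Phi(d / sqrt((1 + 2c)/3)). For c = 0.9 this is 0.78; for c = 0.5 it is 0.82.

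4. *Only one socket's score known (period 1).* With a midpoint cut-off, P(correct) = Phi(d x sqrt(2(1 - rho)) / 2). For rho = 0 this is 0.70, for rho = 0.5 it is 0.65, and for rho = 0.9 it is 0.57. One score alone is a weak clue.

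5. *Effect on one timed test, no true difference, n = 25.* A right guess shifts the paired difference by b and a wrong guess shifts it by -b, so the net shift is (2 x accuracy - 1) x b. At accuracy 0.775 the factor is 0.55; at 0.65 it is 0.30.

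| Assumed b (SD) | Net shift at 0.775 | False-positive rate | Net shift at 0.65 | False-positive rate |
|---|---|---|---|---|
| 0 | 0 | 1.7% | 0 | 1.7% |
| 0.1 | 0.055 | 2.0% | 0.03 | 1.8% |
| 0.2 | 0.110 | 3.2% | 0.06 | 2.1% |
| 0.3 | 0.165 | 5.4% | 0.09 | 2.7% |

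6. *Order of tests.* If the timed tests came first at every visit, the assessor would have no second-socket rating at the three period 1 visits or at the first period 2 visit: 3 + 1 = 4 of 6. At the last two visits the comparison would be available.

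**The case against.** The strongest reply is that several links in the chain are not in the documents.

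- *Mode of administration.* Section 11.4 speaks of administering the measures, not of interviewing. Section 9.3(c) refers to OPUS forms, and section 3.2 requires subjects to read English. Self-completion may already be intended. This stands as a gap in the text, but nothing says that the person administering the forms does not see the answers.
- *Restriction of forms.* Section 25.1 has the PI limit forms to what each person needs. This does not close the route, because the assessor's listed tasks include these very measures.
- *Knowledge of the hypothesis.* Section 11.4 keeps the assessor uninformed beyond the listed tasks. Section 20.2 is a general statement that does not say the assessor attends the meetings or hears the hypothesis. That is fair: the two passages conflict on their face and need reconciling, but they do not show that the assessor knows the expected direction. An assessor who does not know it could still favour the socket that was rated better.
- *Timing and order.* Hand timing is an inference. Section 9.2 describes a spoken start for the T-Test and a rule against touching the sticks, but names no timing device. The numbered list in section 9.2 is not stated to be an order of administration. With three visits per socket, however, ratings from earlier visits are known at later ones whatever the order.
- *Planning effect.* It rests on six persons and a different socket comparison, so the accuracies are illustrative. That ratings carry a clue does not depend on the exact value, only on a real difference in comfort.

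**Conclusion.** The point holds as a weakness in the blinding of the timed tests. One person is given both kinds of measure, the ratings carry information about the socket in the direction the trial expects, and the stated safeguards leave that route open. Under the planning effect the clue is worth about 77% correct guesses once both sockets' scores are known, and 57% to 70% from one socket's score. The false-positive rates of 2.0%, 3.2% and 5.4% per timed test rest on assumed biases of 0.1, 0.2 and 0.3 SD and on 77.5% accuracy for the whole contrast. They show scale and are not a forecast.

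A reader might infer that the blinding is lost altogether, or that the false-positive rate could reach 16%. The documents do not support either reading. Net shifts of 0.1, 0.2 and 0.3 SD would give 2.9%, 7.4% and 16.3%, but if those figures are the bias per guess, these rates require every guess to be right. A reader might also extend the point to the gait hypotheses (2a and 2b) or to the primary endpoint. The stick-figure view largely protects the former, and the latter is rated by subjects who know their socket.

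**What to change.** In sections 9.2 and 11.4:

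- State that subjects complete the Socket Comfort Score and OPUS themselves, out of the assessor's sight.
- Send completed forms directly to the PI file, and withhold them from the assessor until all timed tests and gait processing are finished.
- Remove patient-reported measures from the assessor's tasks.
- Reconcile the uninformed assessor of section 11.4 with the statement in section 20.2 that everyone assisting is informed about the protocol.

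If the assessor must keep administering the ratings, require the timed tests first at each visit. This is only a partial remedy: it leaves no two-socket comparison at the first four of six visits, but the last two, including the second socket's 6-week session, stay exposed.

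The cost is a change of wording. It needs no extra visits or staff and does not alter the sample size or the analysis. The downside is a few missed items on self-completed forms, which a completeness check by already unblinded staff can catch.

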[name] will collect all gait data and contribute to the interpretation of the data. As manager, [name] is responsible for maintenance and operation of the JBVAMC-MARL facility and equipment. [name] has completed all NU and VA IRB required training for human subject research and serves on the new Jesse Brown VA Medical Center IRB.

[name], MS, is a research engineer at the NUPOC who will assume the role of blinded assessor for this study. [name] has completed all IRB required training for human subject research.

[name], CPO, is President and CEO of Scheck & Siress and will help support implementation of the project at Scheck & Siress. [name] is currently undertaking training.

A statistician will be engaged to provide statistical support throughout the project.

20.2 Other resources available to conduct the research:

- Currently, about 1.9 million people are living with limb loss in the United States. A total of 19,864 lower limb amputation procedures were performed in the state of Illinois from 2009 to 2012. A total of 760 transfemoral amputation procedures were performed in 2012.
- We plan to recruit 10 subjects per year for the first 3 years of the clinical trial and 5 in the 4th year for a total of 35. These subjects will be a mix of civilians and Veterans. Given the size of the amputee population in Illinois and the scope of the clinical practice of our collaborators, we believe that this recruitment goal is feasible.
- The key personnel involved in this study will devote the equivalent of a day a week to this research project for the next three years.

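### The stick-figure view does not by itself keep gait processing blind: the processor also tests each subject in person, and no masking of the gait files is stated

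*Combined protocol and SAP*

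**What the plan says.** Section 11.4 makes the assessor the only blinded party and defines the role: "the assessor will remain uninformed in any aspect of the study except administration of performance and patient-reported measures and processing motion analysis data". The staff description ahead of Section 20.2 identifies the research engineer as the person "who will assume the role of blinded assessor for this study". Among its consistency measures, Section 11.4 also lists "having a single person post-process all the data".

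The argument for blind processing is that it is not possible to "tell while processing the motion analysis data what socket the subject was wearing because the data is viewed only as a stick figure". Because marker placement exposes the socket, the assessor stays away from gait capture. For the in-person tests, Section 11.4 relies on clothing to hide the socket and on telling subjects not to disclose it.

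Section 9.2 says that, for each socket, "3 identical data collection sessions will be held", at week 1 and at 3 and 6 weeks, with every measure taken each time. Section 9.1 has two periods, and each subject receives both sockets.

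**The concern.** A stick figure hides the shape of the socket. It does not remove what the person at the screen already knows about that subject in that period. Here that person has also met the subject to give the Socket Comfort Score, the OPUS (which includes satisfaction with the device) and the timed tests. Those conversations are about the socket, and Section 11.4 itself expects one socket to be the more comfortable, so even a subject who follows the instruction may prompt a guess.

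The crossover makes one disclosure go further than it would in a parallel design. With two sockets and two periods, knowing the socket in one period gives the socket in the other.

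At stake are the six gait variables listed in Section 11.1, which are the basis of Hypotheses 2a and 2b. Capture is unblinded by necessity, so processing is the only stage at which these data can be blinded.

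**Working it through.** **Plan's own figure.** The documents give no figure for the risk of unblinding. Their only calculation is the sample size in Section 11.2. A two-sided paired t-test with d = 0.754, alpha 0.05 and power 0.95 needs N = 25, and this reproduces: power is 0.951 at 25 and 0.942 at 24. It concerns the Socket Comfort Score and is used below only as the number of completers.

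**What the documents fix**
- Contacts between assessor and subject: 3 sessions × 2 periods = 6 (Sections 9.1 and 9.2).
- Gait processors: one, the same assessor (Section 11.4).
- Sets of gait files, counting one per visit: 25 × 6 = 150.

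**What they leave open**
- The chance *p* that the assessor learns the socket at a given visit. Assumed here: 0.5% to 10%, independent between visits.
- Whether a file shows subject, visit or period when it is processed.
- When processing takes place relative to the visits.

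**Formulas**
- A: chance of at least one slip in six visits = 1 − (1 − p)^6.
- B: expected number of such subjects among 25 = 25 × A.
- C: exposed files if all are linkable and all are processed after the last visit = 150 × A. This is the upper bound for a given p.
- D: exposed files if all are linkable but each is processed before the next visit = 25 × the sum over k = 1 to 6 of [1 − (1 − p)^k]. Files processed before a slip stay blind.
- E: exposed files if a slip reaches only its own visit's file = 150 × p.

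| p (assumed) | A | B (of 25) | C (of 150) | D (of 150) | E (of 150) |
|---|---|---|---|---|---|
| 0.5% | 3.0% | 0.7 | 4.4 | 2.6 | 0.75 |
| 1% | 5.9% | 1.5 | 8.8 | 5.2 | 1.5 |
| 2% | 11.4% | 2.9 | 17.1 | 10.2 | 3.0 |
| 5% | 26.5% | 6.6 | 39.7 | 24.2 | 7.5 |
| 10% | 46.9% | 11.7 | 70.3 | 44.6 | 15 |

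For example, at p = 5%: A = 1 − 0.95^6 = 0.265 and C = 150 × 0.265 = 39.7. The six terms in D are 0.050, 0.098, 0.143, 0.185, 0.226 and 0.265. They sum to 0.967, and 25 × 0.967 = 24.2.

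Independence matters. If the same subjects tend to give the socket away at every visit, A falls towards p itself.

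**Whether another section closes the gap**
- Section 11.3 assigns a study code at enrollment, has the clinical collaborators' forms carry only that code, and keeps the master list locked with the PI. A study code hides identity but not period, and no rule is given for gait files.
- Section 25.1 has the PI limit what each staff member sees on data collection forms. It does not mention motion files.
- Sections 10.1 and 11.3 describe de-identified data in RedCap for statistical analysis, which comes after gait processing.

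None states that gait files are relabelled or shuffled, or that suspected unblinding is recorded.

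**The case against.** The strongest reply is that the quoted sentence concerns only what can be seen during processing, and on that it may well be right. In-person contact is handled separately, through clothing, the instruction to subjects, absence from capture, and keeping the assessor otherwise uninformed. These are real safeguards, and they stand. They lower the chance of a slip, but they do not limit what a slip reaches once it has happened.

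A reader might infer that one slip unblinds all six of a subject's gait files. The documents do not support that. It would need every file to be linkable to subject and period, and every file to be still unprocessed at the time of the slip. The plan states neither. Column D shows how much visit-by-visit processing reduces the exposure.

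A reader might also infer that knowing the socket would change particular processing decisions, such as marker clean-up or the choice of strides. The documents do not describe the processing steps or how much judgement they involve, and the figure of the processing window is not in the text available. The route to bias is plausible, but its size is unknown.

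Finally, gait is a secondary endpoint. A slip would also affect the timed tests, which the assessor gives directly and which file masking cannot protect. Both points are right and limit the weight of the concern. They do not supply the missing masking.

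**Conclusion.** The concern holds in a limited form. The stick-figure argument does not by itself secure blind processing, because the single processor also meets each subject at up to six visits. A socket learned or guessed at one visit can unblind that subject's gait files that are not yet processed, if those files can be linked to subject and period. Nothing in the documents prevents such linkage.

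Under the assumed slip rates, the chance of at least one slip per subject is 3% to 47%. That bounds the exposure of the subject's files from above. It is not an estimate of bias, and no shift in the gait variables can be derived. The conclusion that masking is missing does not depend on the assumed rates; only the size does.

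The Socket Comfort Score analysis and N = 25 are unaffected. This is a cheap improvement to the data behind Hypotheses 2a and 2b, and it does not challenge the trial's main conclusion.

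**What to change.** In Section 11.4, keep the existing safeguards and add file masking:

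- The gait laboratory manager, who already captures the data, checks quality at capture and exports each file under a random code that shows neither subject, visit nor period.
- The PI or the statistician holds the key.
- The assessor processes coded files in mixed order across subjects and periods.
- Codes are broken only after processing is locked.
- Any suspected unblinding of the assessor is logged, with the visit at which it arose.

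Processing need not wait for each subject's last visit, provided that each batch mixes subjects and periods.

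The cost is file renaming, a code list kept by existing staff, and somewhat later gait results. Sample size, visits and subject burden do not change. The change does not blind marker placement or capture, and it does not protect the timed tests; the log would at least show how often those were at risk.
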